### 2.4.2.2 Compliance for CNI/EVR:

To evaluate patient compliance for CNI/EVR, CNI/EVR trough levels will be imputed (see [Section 4.2.2](#) for details) for each day from the date of the first dose of the respective study drug (CNI/EVR) to the maximum study drug on-treatment date, which is defined as the minimum of (the date of the last study drug dose plus two days or the last contact day). For each day, patient compliance will be assessed by comparing the imputed trough level with the corresponding

target trough level range. If a patient was compliant for at least 70% of days on study, then this is a compliant patient.

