Control regimen	Drug regimen used post-randomization as a comparator to evaluate comparative effects of the investigational drug (i.e. the combination of MPA and a CNI- either tacrolimus or cyclosporine)		
Enrollment	Point/time of subject entry into the study; the point at which informed consent must be obtained (i.e. prior to starting any of the procedures described in the protocol)		
Extension	Study period from Month 12 visit to completion of Month 24 visit regardless of treatment status (i.e. can be on or off randomized regimen)		
Investigational regimen	The investigational drug regimen tested in the study post-randomization (i.e. the combination of everolimus and a CNI- either tacrolimus or cyclosporine)		
Lost to follow-up	Those subjects whose status is unclear because they fail to appear for study visits without stating an intention to withdraw and cannot be contacted		
Subject Number	A number assigned to each subject who enrolls into the study		
Period	A distinct stage in the subjects' participation in the study, each period serves a purpose in the study as a whole		
Premature subject withdrawal	Point when the subject exits from the study prior to the planned completi of all assessments, synonymous with study discontinuation, not the sam as treatment discontinuation		
Primary Treatment Period	Study period from randomization to completion of Month 12 visit, regardless of treatment status (i.e. can be on or off randomized regimen)		
Screening period	Period from signing informed consent to successful completion of the transplant procedure		
Study Completion	Point at which the subject came in for a final evaluation visit at Month 24 or complete discontinuation from the study if prior to Month 24		
Study drug/ treatment	Any single drug or drug regimen administered to the subject as part of the required study procedures in any study period, includes everolimus, tacrolimus, cyclosporine, basiliximab, MPA and corticosteroids		
Treated biopsy proved acute rejection (tBPAR)	An acute rejection episode documented by histological evidence for which anti-rejection therapy (e.g. steroids, antibody or increase in study regimen immunosuppression) was given.		
Treatment discontinuation	Point when subject permanently stops taking study/investigational or control treatment drug/regimen for any reason, not the same as study discontinuation/premature subject withdrawal		

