2.2 Secondary objectives

Key Secondary Objectives

- To evaluate everolimus with reduced exposure CNI compared to MPA plus standard exposure CNI at 12 months post-transplantation with respect to the composite efficacy failure rate of (treated biopsy proven acute rejection (tBPAR), graft loss or death).
- To evaluate the binary composite endpoint of tBPAR or eGFR < 50 mL/min/1.73m² (MDRD4) Month 12 among compliant subjects.

Other Secondary Objectives

To evaluate, by treatment group;

- The incidence of composite endpoint of tBPAR or eGFR < 50 mL/min/1.73m² (MDRD4) at Month 24.
- The incidence of composite endpoint of tBPAR (excluding Banff grade 1A acute rejections) or eGFR < 50 mL/min/1.73m² (MDRD4) at Month 24.
- The incidence of composite endpoint of tBPAR or eGFR < 50 mL/min/1.73m² (MDRD4) at Month 12 by subgroup (see Section 9.4.4).

- The incidence of composite endpoint of tBPAR, graft loss or death at Month 24.
- The incidence of composite endpoint of tBPAR, graft loss, death, or loss to follow-up at Months 12 and 24.
- The incidence of composite endpoint of tBPAR, graft loss, death or eGFR < 50 mL/min/1.73m² at Months 12 and 24.
- The incidence of composite endpoint of graft loss or death at Month 12 and 24.
- The incidence of individual endpoints of death, graft loss, tBPAR, BPAR, tAR, AR and humoral rejection at Months 12 and 24.
- The incidence of tBPAR by severity and time to event.
- The incidence of tBPAR excluding Banff 1A grade acute rejections
- The incidence of transplant recipients with eGFR < 50 mL/min/1.73m² at Months 12 and 24.
- Renal allograft function and change in renal allograft function from Month 1 (eGFR) at Months 12 and 24.
- The evolution of renal function, as eGFR, over time by slope analysis.
- Renal function by Cystatin C-based and other alternate formulae (e.g. CKD-EPI).
- The incidence of adverse events, serious adverse events and adverse events leading to study regimen discontinuation.
- The incidence of CMV and BKV, new onset diabetes mellitus, chronic kidney disease with associated proteinuria and CNI associated adverse events.
- Urinary protein and albumin excretion by treatment estimated by urinary protein/creatinine and urinary albumin/creatinine ratios.
- The incidence of major cardiovascular events.
- The incidence of malignancies.

3 Investigational plan

[figure not shown]

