5.5.5 Permitted dose adjustments and interruptions of study treatment

For all everolimus subjects who are unable to tolerate the protocol-specified dosing schedule, dose adjustments are permitted in order to keep the subject on investigational drug. The following guidelines should be followed (Table 5-2), for management of lipid elevations refer to Section 5.5.7 for initial approach, prior to considering dose reduction. The everolimus dose should be decreased by at least 0.25 mg b.i.d if a dose reduction is necessary. If a temporary reduction in everolimus level is needed, the everolimus trough blood level should still be maintained no lower than 3 ng/mL. Everolimus should be discontinued if a trough level \geq 3 ng/mL cannot be maintained due to toxicity. Severe and unremitting changes may also lead to investigational drug discontinuation.

For subjects having rATG administered, whether as induction therapy, DGF or anti-rejection treatment the relative impact of all medications to reduced hematological parameters should be considered, thus everolimus dose reduction to these guidelines may not always be necessary under these circumstances.

Table 5-2 Guidelines for everolimus dose reduction/interruption

	Platelet count (/mm³)	Hemoglobin (g/dL)	WBC count (/mm³)	Cholesterol (mmol/L)	Triglycerides (mmol/L)
Dose reduction	≤ 75000	≤ 8	≤ 3000	> 9	> 8.5
Interruption	≤ 50000	≤ 6	≤ 2500	≥ 10	≥ 10.5

If everolimus is interrupted for safety reasons for longer than 21 consecutive days study regimen should be discontinued. Everolimus may be interrupted during antibody treatment of rejection episodes. In case of any planned or emergency surgery during the study treatment period, everolimus can be interrupted and a compensatory increase in CNI may be considered. In elective cases, this may be done 5 days before surgery which would allow restart of everolimus by 21 days post-surgery, in these cases everolimus must be re-introduced at the latest by day 27 after discontinuation.

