## 2.4.2 Compliance

### 2.4.2.1 Compliance for MPA

For each day, a patient is compliant to MPA as long as this patient takes MPA (non-compliant when MPA was off). If a patient is compliant for at least 70% of days on study, then this is a compliant patient.

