### 2.12.1 Futility Analysis

Although the primary study endpoint (the composite of tBPAR or eGFR (MDRD4)  $< 50$  ml/min/1.73m^2) is at Month 12, the futility analysis will be based on the endpoint at 6 months. In kidney transplant trials, typically most tBPAR events (e.g. 80% in A2309 study) occur within the first 6 months, and eGFR at Months 6 and 12 are very similar (e.g. in A2309 study, the mean eGFR was 57.2 at Month 6 vs. 56.3 at Month 12 in the everolimus 1.5 mg group). Therefore, it is expected that the 6-month endpoint will be a good predictor of the 12-month endpoint.

The futility of the non-inferiority for the primary endpoint will be assessed via conditional power together with 95% prediction interval. Conditional power is the probability of rejecting the following null hypothesis given the observed data from the futility analysis patients (6-month completers) and assumptions on the data from future patients. In conjunction with the conditional power, a prediction interval will be calculated to estimate the potential treatment effect and its associated precision (See the calculations of the conditional power and prediction interval in [Section 2.12.3](#)).

$H_{01}$ :  $R_{EVR+tCNI} - R_{MPA+sCNI} \geq 0.10$  (non-inferiority margin): the difference in proportion of patients experiencing tBPAR or eGFR (MDRD4)  $< 50$  mL/min/1.73m^2 at 6 months between the everolimus plus reduced CNI ( $R_{EVR+tCNI}$ ) and the MPA plus standard CNI arm ( $R_{MPA+sCNI}$ ) is at least 10%, vs.

$H_{A1}$ :  $R_{EVR+tCNI} - R_{MPA+sCNI} < 0.10$  (non-inferiority margin): The difference in proportion of patients experiencing tBPAR or eGFR (MDRD4)  $< 50$  mL/min/1.73m^2 at 6 months between the everolimus plus reduced CNI ( $R_{EVR+tCNI}$ ) and the MPA plus standard CNI arm ( $R_{MPA+sCNI}$ ) is less than 10%.

For the futility analysis, the incidence rate of the composite endpoint of tBPAR or eGFR (MDRD4)  $< 50$  ml/min/1.73m^2 will be assessed for each arm for the **6-month completers**. The 6-month completers are defined as follows:

- ~30% of the total randomized patients who have reached Month 6 or discontinued from study early (note: For those patients who were beyond Month 6 in the study, tBPAR up to Month 12 and eGFR (MDRD4) at Month 12 will be used instead if they are available at the time of the futility analysis).

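### SAP 2.4.2 scores compliance past a rejection, so what follows treatment of a tBPAR can remove that failure from the compliant-set analysis

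*SAP*

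**What the plan says.** **Use of the set.** SAP 2.2 defines the compliance set as the full-analysis-set (FAS) patients who comply with both their CNI and their EVR or MPA. SAP 2.5.4.1 repeats the primary-endpoint analysis (tBPAR or eGFR < 50) on it. Protocol 2.2 lists this endpoint at "Month 12 among compliant subjects" among the key secondary objectives. SAP 2.6.1 names only tBPAR, graft loss or death as key secondary and files the compliant-set analysis as supportive.

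**CNI and EVR (SAP 2.4.2.2).** Each day's imputed trough is compared with the target range. Imputation runs from first dose to a maximum on-treatment date, "which is defined as the minimum of (the date of the last study drug dose plus two days or the last contact day". The 70% rule follows: "If a patient was compliant for at least 70% of days on study, then this is a compliant patient".

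**MPA (SAP 2.4.2.1).** On any day, "a patient is compliant to MPA as long as this patient takes MPA (non-compliant when MPA was off". Then: "If a patient is compliant for at least 70% of days on study, then this is a compliant patient".

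Neither rule mentions rejection, and the CNI ranges in SAP Table 2-2 carry no post-rejection exemption.

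**Treatment of rejection.** The protocol glossary defines a tBPAR as one for which "anti-rejection therapy (e.g. steroids, antibody or increase in study regimen immunosuppression) was given". Protocol 5.5.5 adds: "Everolimus may be interrupted during antibody treatment of rejection episodes". Protocol 5.5.9 lists lack of efficacy as a reason for stopping study treatment.

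**The concern.** A tBPAR is a failure on the endpoint being analysed. If its treatment leads to a long spell outside target, or off MPA, the patient can fail the 70% rule because of the failure and then leave both numerator and denominator. Membership of the set is then partly a consequence of the outcome.

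This lowers event rates in the set. It distorts the treatment difference if rejecters are removed more often in one arm, or if tBPAR rates differ between arms. At stake is a protocol key secondary objective that would be read as support for the non-inferiority claim.

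**Working it through.** **Inputs from the documents.** Compliance threshold 70% of days (SAP 2.4.2). One month is 30 days (Protocol Table 6-1 notes), so 12 months is 360 days. Planned composite rate 50% per arm and margin 10 points (Protocol 9.7). On timing, SAP 2.12.1 states that "typically most tBPAR events (e.g. 80% in A2309 study) occur within the first 6 months".

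**Inputs assumed.** The tBPAR rate t, and the share f of tBPAR patients who lose compliant status. The documents give neither.

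**The plan's own figure.** No rate or power is stated for the compliant set. As a check on the 50% and 10-point inputs, non-inferiority power Φ(0.10/√(2·0.5·0.5/n) − 1.96) gives 99.5, 98.1, 96.6, 95.1 and 92.2% for n = 1020, 816, 714, 653 and 571. Protocol Table 9-1 has >99, 98, 97, 95 and 92.

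**Step 1: days needed to lose compliant status.** A patient otherwise always in target must be non-compliant on more than 0.30 × 360 = 108 days. If every day after a rejection on Day d is non-compliant, the condition is (360 − d)/360 > 0.30, so d < 252. A rejection by Day 180 leaves at least 180 days, which is room enough. Whether those days are actually out of target is a separate question.

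**Step 2: which routes can supply those days.**
- *CNI increase.* In SAP Table 2-2 the top of each EVR-arm range is below the bottom of the MPA-arm range. Tacrolimus (ng/mL): 4-7 vs 8-12, 2-5 vs 6-10, 2-4 vs 5-8. Cyclosporine (ng/mL): 100-150 vs 200-300, 50-100 vs 150-200, 25-50 vs 100-200. A level raised into the MPA-arm range is out of target for an EVR patient and in target for an MPA patient.
- *How long it counts.* SAP 4.2.2 fills each gap backward from the next measured trough. With scheduled troughs only, the Month 6, 9 and 12 values cover 60, 90 and 90 days. Any two out of range give 150 to 180 days (42 to 50%), more than 108.
- *Short everolimus hold.* Interruption is generally limited to 21 consecutive days: 21/360 = 5.8%. The trough imputation does not score hold days directly either. This alone removes nobody who is otherwise compliant.
- *Stopping CNI or EVR at the rejection.* If the denominator is the imputed window, about two days are added and the pre-rejection score stands. If it is all days on study, the later days could count against the patient.
- *Stopping MPA at the rejection.* Off-drug days are non-compliant, so Step 1 applies directly if days on study run to Month 12.

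**Step 3: effect on the comparison.** With composite rate R = 0.50 in both arms, and otherwise outcome-neutral membership, the compliant-set rate is (R − t·f)/(1 − t·f).

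| t | f, one arm vs the other | Rates | Difference (points) |
|---|---|---|---|
| 0.10 | 0.6 vs 0.3 | 46.8% vs 48.5% | −1.6 |
| 0.10 | 0.8 vs 0.3 | 45.7% vs 48.5% | −2.8 |
| 0.15 | 0.6 vs 0.3 | 45.1% vs 47.6% | −2.6 |
| 0.15 | 0.8 vs 0.3 | 43.2% vs 47.6% | −4.5 |

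Reversing the fractions reverses the sign. Equal t and equal f give zero.

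**Step 4: equal removal does not protect a real difference.** Suppose EVR truly has 5 points more tBPAR (15% vs 10%; composite 55% vs 50%) and f is equal. At f = 0.5 the difference is 0.475/0.925 − 0.45/0.95 = 4.0 points. At f = 1 it is 0.40/0.85 − 0.40/0.90 = 2.6 points. The true difference is 5.0.

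**The case against.** The strongest reply is that the protocol works against long out-of-target spells. Sections 5.5.4 and 3.6 require CNI and everolimus to be kept in range, a repeat trough 5 ± 2 days after a dose change, and sponsor alerts to centres about out-of-range values. The operative text in 5.5.5 treats rejection with bolus methylprednisolone; the regimen increase is one example in a glossary entry, and an increase can also bring a low trough back into target. Any set built on post-randomisation compliance shares this weakness. The compliant set also carries no hypothesis in the testing hierarchy.

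This limits how often the problem arises, but not whether it can. No rule stops scoring at the event, and the non-overlapping CNI ranges treat the same level differently by arm.

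A reader might infer more, and the documents do not support it:
- *That any rejection treatment costs compliant status.* A hold of 21 days does not, and steroids with troughs kept in range do not.
- *That the 80% of tBPAR seen in the first 6 months would be removed.* That figure gives timing only. Removal needs sustained out-of-target or off-drug days, which no section says will follow.
- *That the rule favours everolimus.* The CNI ranges point towards more removal in the EVR arm. The off-drug rule for MPA can point the other way. The net direction is unknown.

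**Conclusion.** The concern holds as a defect in one analysis. SAP 2.4.2 lets events after a tBPAR decide whether that tBPAR is counted in the compliant set, chiefly through a sustained CNI increase and, in the MPA arm, through stopping MPA. The window is also inconsistent: CNI/EVR troughs are imputed only to two days after last dose, MPA off-drug days count as non-compliant, and both rules refer to days on study. Whether stopping CNI or EVR counts against a patient therefore depends on an unstated denominator.

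The 1.6 to 4.5 points rest wholly on the assumed tBPAR rates (10-15%) and removal fractions (60-80% vs 30%). They illustrate what is possible and are not an estimate. A reader might infer that the primary non-inferiority conclusion is at risk. It is not: that analysis is on the FAS with post-discontinuation data, and none of the three hierarchical tests uses the compliant set.

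**What to change.** In SAP 2.4.2:

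1. State one denominator and one rule for off-drug days, identical for CNI, EVR and MPA.
2. Add a pre-specified compliant-set analysis in which scoring ends the day before the first tBPAR or graft loss. Patients whose event precedes the first scheduled trough (Week 1) stay in the set. Any Month 24 compliant-set analysis (SAP 2.7.2.1) needs the matching end date.
3. Report by arm how many tBPAR patients the 70% rule excludes.

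The cost is SAP wording and a modest derivation change, since SAP 4.3 already derives the tBPAR and graft-loss dates. There are three downsides to acknowledge. Early-event patients are classified on few days, and window length then depends on the event, so this should sit beside the existing definition rather than silently replace it. Counting all off-drug days to Month 12 could exclude CNI/EVR patients who stop for any reason, so that choice must be explicit. Outcome dependence through eGFR < 50 remains: that component has no event date, and nephrotoxicity can itself prompt a CNI reduction (Protocol 5.5.4).

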### 2.4.3 Prior/Concomitant Medication

Medications will be identified using the NovDTD including Anatomical Therapeutic Chemical (ATC) code. Prior medications are defined as drugs taken prior to the first dose of randomized study medication regardless of whether they continue thereafter. Any medication given at least once between the date of the first dose and the last dose of randomized study medication will be defined as concomitant medication, including those started before randomization and continued into the treatment period. Any medication started after the discontinuation of randomized study medication will not be considered as concomitant medication. Prior or concomitant medication will be identified based on recorded or imputed start and end dates. Rules for imputing incomplete (start and end) dates are described in [Section 4.2.4](#).

Prior and concomitant medications will be summarized by treatment group and total in separate tables for SAF. Medications will be presented in alphabetical order, by ATC codes and grouped by *anatomical main group* (the 1st level of the ATC codes). Tables will show the overall number and percentage of patients receiving at least one drug within a particular ATC code and at least one drug in a particular anatomical main group.

#### 2.4.3.1 Steroids

Steroids will be displayed using prednisone equivalent body weight adjusted doses. The doses displayed in the following table are considered equivalent. To determine prednisone equivalent doses, doses will be multiplied by the conversion factor shown in [Table 2-2](#). To adjust the dose, the body weight measured closest to the start of a steroid dose will be used (from vital signs eCRF).

**Table 2-3 Steroids conversion factors**

WHO drug code	Preferred Term Corticosteroid	Equivalent Dose [mg]	Conversion Factor
000447xx	Prednisone	5	1
000162xx	Prednisolone	5	1
000496xx	Methylprednisolone	4	1.25
012428xx	Meprednisone	4	1.25
001867xx	Prednylidene	40/7	0.875
000319xx	Triamcinolone	4	1.25
000146xx	Cortisone	25	0.2
000286xx	Hydrocortisone	20	0.25
002131xx	Fludrocortisone	2	2.5
000085xx	Betamethasone	0.75	20/3
000664xx	Paramethasone	2	2.5
000160xx	Dexamethasone	0.75	20/3
008827xx	Deflazacort	6	5/6
006445xx	Cloprednol	3	5/3

Average daily doses and body weight-adjusted average daily doses by visit window will be summarized for corticosteroids (expressed in doses equivalent to prednisone) for each treatment group for patients who are on study medication.

### 2.4.3.2 Immunosuppressive Therapies

All immunosuppressive medications will be summarized by ATC code, WHO preferred term and treatment group as follows:

- Concomitant other than study medication (cyclosporine, everolimus, tacrolimus & MPA)
- Taken after early discontinuation of randomized study medication

### 2.4.3.3 Lipid-Lowering Drugs

Any medication with ATC code C10A will be considered lipid-lowering drugs. Lipid-lowering agents will be grouped by ATC code and summarized by WHO preferred terms. For any of these medications, the number of patients (and percentage) receiving at least one dose *concomitantly* with randomized study medication will be displayed; this will not include any drugs started after the discontinuation of study medication.

## 2.5 Analysis of Primary Objective

### 2.5.1 Primary Endpoint

The primary efficacy variable is a binary composite endpoint of tBPAR or eGFR (MDRD4) < 50 mL/min/1.73m^2 at Month 12 post-transplantation. The component of eGFR (MDRD4) < 50 mL/min/1.73m^2 at Month 12 is defined as the incidence of eGFR (MDRD4) < 50 mL/min/1.73m^2 in the Month 12 visit window.

### 2.5.2 Statistical Model, Hypothesis, and Method of Analysis

The primary analysis will be performed on the Full Analysis Set following the intent-to-treat principle.

#### Testing of CNI effects:

Based on FAS without imputation, treatment by CNI interaction for the composite endpoint of tBPAR or eGFR (MDRD4) < 50 mL/min/1.73m^2 will be assessed using a logistic regression model including covariates/factors for treatment, CNI, region, interaction of treatment and CNI, interaction of treatment and region, donor type, HLA mismatch ( $\leq 3$  vs  $> 3$ ), induction therapy, recipient gender, recipient age, donor age, DGF, and eGFR (MDRD4) at Month 1. In the model, recipient and donor age will be treated as continuous variables. If the interaction is not significant at the level of 0.10, i.e. the effects of treatment are similar for each CNI, then the primary analysis will be based on the pooled CNIs, i.e. everolimus plus reduced CNI (EVR+rCNI) vs. MPA plus standard CNI (MPA+sCNI). If this test shows significantly different event rates for tacrolimus vs. cyclosporine, then testing will be performed for the 2 CNIs separately, with the tacrolimus subgroup being considered primary [REDACTED]

